12.5 Analysis of secondary endpoints

12.5.1 Efficacy and/or Pharmacodynamic endpoint(s)

All secondary efficacy analyses will be based on the FAS. The analyses performed at eye level will focus on the study eye only.

The secondary efficacy objective and endpoints of this study are as follows:

To evaluate the effect of brolucizumab on the evolution of qualitative and quantitative OCTA parameters of wAMD from Baseline to Week 48

Summary statistics of each parameter assessed by OCTA, of which the main quantitative parameters are CNV flow size and vessel density, and the main qualitative ones are branching vessels, peripheral anastomotic arcades, vascular loops and dark halo, from Baseline up to Week 48 will be provided, including changes vs Baseline. Paired t-test or Wilcoxon signed rank test, based on data distribution, will be used to test the difference at each time point vs Baseline for continuous parameters. In case of a dichotomous parameter, a McNemar test will be used.

To evaluate the effect of brolucizumab on the evolution of qualitative and quantitative SD-OCT parameters of wAMD from Baseline to Week 48

Summary statistics of each parameter assessed by SD-OCT, of which the main quantitative parameters are CRT and PED volume, and the main qualitative ones are IRF, SRF, sub-RPE fluid, status of ELM, SHRM and outer retinal tubulation, from Baseline up to Week 48 will be provided, including changes vs Baseline.

Paired t-test or Wilcoxon signed rank test, based on data distribution, will be used to test the difference at each time point vs Baseline for continuous parameters. In case of a dichotomous parameter, a McNemar test will be used.

To evaluate the effect of brolucizumab on the evolution of functional parameters of wAMD from Baseline to Week 48

Summary statistics of BCVA from Baseline at each visit up to Week 48 as well as changes vs Baseline will be provided. Paired t-test or signed rank test, based on data distribution, will be used to test the difference at each time point vs Baseline.

Frequency of patients with an improvement of at least 5/10/15 letters or worsening will be also provided.

To evaluate the effect of brolucizumab on sustained dryness from Baseline to Week 48

- Time to reach sustained dryness of the study eye, as defined by the absence of IRF and SRF for at least 2/3 consecutive visits, will be descriptively summarized. Survival Kaplan-Meier curve will also be provided including summary estimates.

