1.1. Changes from The Study Protocol

For SD-OCT parameters, in the study protocol, the Volume of Pigment-Epithelium Detachment (PEDs) defined as irregularly elevated lesions produced by the growth of the choroidal neovascular membrane and the accumulation of fluid or material in the sub-RPE space is planned to be evaluated as continuous variable (quantitative parameter). However, it was not possible to measure this volume according to the CRC evaluation. Consequently, the following qualitative parameters will be provided by CRC: the presence of PED will be summarized considering the possible values (i.e., 'No', 'Yes', 'UNG/P', 'UNG/Q') and in case of PED presence, a description of the type of PED will be provided considering the predominant feature as fibrovascular only, predominantly fibrovascular, purely serous, predominantly serous, drusenoid PED, UNG/P, UNG/Q.

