| 
Secondary objective(s):
 
1. To evaluate the effect of brolucizumab on the evolution of qualitative and quantitative OCTA parameters of wAMD from Baseline to Week 48
 | 
1. OCTA qualitative parameters graded by CRC:
 
 • Branching vessels • Peripheral Anastomotic Arcades • Vascular Loops • Dark Halo • Presence CNV lesion and its involvement of the foveal center 
1. OCTA quantitative parameters graded by CRC:
 
 • CNV flow size including Total CNV lesion area (mm²) and Greatest linear diameter of lesion (mm) • Vessel density of the lesion including CNV vascular density (%) | 
Secondary endpoint(s):
 
1. Change in OCTA features assessed by qualitative (branching vessels, peripheral anastomotic arcades, vascular loops and dark halo) and quantitative criteria (CNV flow size, and vessel density) from Baseline up to Week 48
 |
| 
2. To evaluate the effect of brolucizumab on the evolution of qualitative and quantitative SD-OCT parameters of wAMD from Baseline to Week 48
 | 
2. SD-OCT qualitative parameters graded by CRC:
 
 • Intraretinal fluid (IRF) including the subcategories: (1) IRF in center 1 mm and (2) IRF at foveal center. • Subretinal fluid (SRF) including the subcategories (1) SRF in center 1 mm and (2) SRF at foveal center. • Sub-retinal pigment epithelium (sub-RPE) fluid including the subcategory sub-RPE in center 1 mm | 
2. Change in SD-OCT features assessed by qualitative (IRF, SRF, sub-RPE fluid, status of ELM, SHRM, outer retinal tubulation and presence and type of PED) and quantitative criteria (CRT) from Baseline up to Week 48
 |

| | |
|--|---|
| | Statistical Analysis Plan |
| | Sponsor: Novartis Protocol: CRTH258AIT04 |

| OBJECTIVES | VARIABLES | ENDPOINTS |
|--|--|--|
| | 
 • Subretinal Hyperreflective Material (SHRM) including the subcategories (1) SHRM in center 1 mm and (2) SHRM at foveal center. • Outer Retinal Tubulation (ORT) including the subcategory ORT in center 1 mm • Status of the ELM as an indicator of retinal integrity considering ELM integrity loss in center 1 mm • Presence and type of PED 
2. SD-OCT quantitative parameters graded by CRC:
 
 • Center Subfield Thickness (CST) | |

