For all qualitative variables except Branching vessels (excluded since this variable provided as result the comparison to the previous read and not a status at each visit), shift table of each post-baseline visit vs Baseline will be provided. A McNemar test Test will be used to test the difference at each post-baseline visit vs baseline. Of note, shift tables will be provided considered only patients for whom baseline and post-baseline value are both available (i.e., parameter considered equal to 'No' or 'Yes').

Data handling rules

An observed approach will be considered for all the analysis.

Sensitivity of secondary analysis

Not applicable.

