- In the study protocol, the Volume of Pigment-Epithelium Detachment (PEDs) defined as irregularly elevated lesions produced by the growth of the choroidal neovascular membrane and the accumulation of fluid or material in the sub-RPE space. On SD-OCT, PEDs appear as broad elevations of the RPE

| | |
|--|----------------------------------|
| | Statistical Analysis Plan |
| | Sponsor: Novartis |
| | Protocol: CRTH258AIT04 |

band relative to Bruch's membrane. The volume of PEDs is considered as a quantitative parameter evaluated by SD-OCT. However, it was not possible to measure this volume according to the CRC evaluation. Consequently, the following qualitative parameters will be provided: the presence of PED will be summarized considering the possible values (i.e., 'No', 'Yes', 'UNG/P', 'UNG/Q') and in case of PED presence, a description of the type of PED will be provided considering the predominant feature as fibrovascular only, predominantly fibrovascular, purely serous, predominantly serous, drusenoid PED, UNG/P, UNG/Q.

In addition, the following quantitative parameter will be measured:

- Central Retinal Thickness (CRT) measurement, as main quantitative morphological parameter of wAMD. The CRT evaluated in this study represents the average retinal thickness of the circular area within 1 mm diameter around the foveal center and it will be called as Center Subfield Thickness (CST) also known as foveal thickness and it will be measured in μm .

Analysis methodology

Firstly, a description for the SD-OCT images' quality will be provided at each visit reporting the proportion of images with quality concerns present and a description of the issue detected that could be one or more of the following:

- HIGH SPEED NOT HIGH RESOLUTION
- VOLUME SCAN ABSENT
- VOLUME SCAN INCOMPLETE
- RASTER/LINE SCAN ABSENT
- RASTER/LINE SCAN INCOMPLETE
- OFF-FOVEA
- MOTION ARTIFACT
- SCAN CLIPPING
- DEGRADED IMAGE
- POOR CONTRAST
- OTHER/ADDITIONAL DETAILS

Similarly, the proportion of images with quality concerns that prevent any grading is provided together with the issue(s) detected (one or more than one among the list previously described).

All qualitative and quantitative parameters described above will be described overall at each visit in terms of absolute and relative frequencies or as continuous variable, respectively.

| | |
|--|----------------------------------|
| | Statistical Analysis Plan |
| | Sponsor: Novartis |
| | Protocol: CRTH258AIT04 |

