For quantitative variables (i.e., CST (μm)), absolute changes from baseline will be computed and summarized at each visit. A paired t-test or Wilcoxon signed rank test, based on data distribution, will be used to test the difference at each time point vs Baseline. A spaghetti plot of CST values at each timepoint will be provided by type of predominant CNV lesion (of note, 'UNG/Q' and 'UNG/P' evaluation of predominant CNV lesion will be considered in a unique category 'Ungradable').

CST will also be described considering only patients with BCVA ETDRS score lower than 69 letters at baseline in terms of descriptive statistics together with absolute changes from baseline and by means of spaghetti plot.

For the qualitative variables IRF, SRF, sub-RPE, SHRM, ORT and ELM integrity loss a shift table of each post-baseline visit vs Baseline will be provided. A McNemar test will be used to test the difference at each post-baseline visit vs baseline. Of note, shift tables will be provided considered only patients for whom baseline and post-baseline value are both available (i.e., parameter considered equal to 'No' or 'Yes') and moreover, the measurements of these qualitative parameters in center 1 mm and at foveal center will not be considering for shift tables.

Data handling rules

An observed approach will be considered for all the analysis.

Sensitivity of secondary analysis

Not applicable.

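### Change in PED presence is part of secondary endpoint 2, but SAP 6.3.2.2 omits it from the shift-table and McNemar list without a reason, so within-eye change in PED presence is analysed nowhere

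*SAP*

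**What the plan says.** **Endpoint.** The SAP section 2 table defines secondary endpoint 2 as change in SD-OCT features. Its list of features ends with "outer retinal tubulation and presence and type of PED) and quantitative criteria (CRT) from Baseline up to Week 48".

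**Why presence and type are there.** The protocol planned PED volume as a quantitative parameter. SAP 1.1 reports that "it was not possible to measure this volume according to the CRC evaluation", and substitutes two qualitative variables: presence of PED and, where present, its type.

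**Protocol rule.** For SD-OCT parameters, protocol 12.5.1 plans changes versus Baseline, with a paired t-test or Wilcoxon signed rank test at each time point for continuous parameters. It then says: "In case of a dichotomous parameter, a McNemar test will be used". No exception is named.

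**What SAP 6.3.2.2 gives PED.** On grading, "the presence of PED will be summarized considering the possible values (i.e., 'No', 'Yes', 'UNG/P', 'UNG/Q". On analysis, "All qualitative and quantitative parameters described above will be described overall at each visit in terms of absolute and relative frequencies".

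**What SAP 6.3.2.2 gives the other qualitative variables.** "For the qualitative variables IRF, SRF, sub-RPE, SHRM, ORT and ELM integrity loss a shift table" is planned for each post-baseline visit against Baseline, followed by a McNemar test at each of those visits. PED is not in this list.

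**The concern.** An endpoint defined as change from Baseline needs a within-eye comparison. Frequencies at each visit show net movement: the share of eyes with a PED at Baseline and later. They do not show how many eyes lost a PED, how many gained one, or whether the balance exceeds chance. With volume gone, presence and type are all the trial has on how PED evolves under treatment, and change in presence is the part the protocol's McNemar rule was written to cover.

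The gap looks like an oversight. When PED moved from the quantitative to the qualitative group it lost its paired t-test or Wilcoxon test, and it was not added to the qualitative list that would have given it a McNemar test.

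**Working it through.** The point rests on the text; no figure in the plan has to be reproduced.

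**Step 1. Is PED presence the kind of variable the list covers?** SAP 6.3.2.2 grades IRF, SRF, sub-RPE fluid, SHRM, ORT and ELM integrity loss as No, Yes, UNG/P or UNG/Q. PED presence has the same four values. The shift tables use only eyes graded No or Yes at both visits, so within them PED presence is dichotomous, as the listed variables are.

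**Step 2. Is a reason given for leaving it out?** Elsewhere the SAP states its exclusions. In 6.3.2.1, branching vessels are left out of the OCTA shift tables: "excluded since this variable provided as result the comparison to the previous read and not a status at each visit". In 6.3.2.2, the centre-1-mm and foveal-centre sub-measurements are expressly left out. Nothing is said about PED, and the branching-vessel reason does not fit, because PED presence is a status at each visit.

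**Step 3. Is the paired analysis supplied elsewhere?** In part, for type only. The SAP 6.3.1 predictor table builds a within-eye change variable for type of PED, comparing Baseline with the last measurement up to Week 16. It is tabulated by responder status and given its own logistic model. Three limits stop it from serving the secondary endpoint:
- it ends at Week 16, whereas the endpoint runs to Week 48;
- it has no category for PED absent, gained or lost;
- its categories do not include purely serous PED, one of the five types in 6.3.2.2.

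Change in presence has no counterpart anywhere.

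**Step 4. Do by-visit frequencies carry the same information?** No. The documents give no PED prevalence, so the counts below are assumed. They take all 122 enrolled patients as complete pairs, which is the upper bound, with PED in 98 eyes at Baseline. That leaves 122 − 98 = 24 eyes without one.

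Later count = 98 − lost + gained. Exact McNemar p = 2 × P(X ≤ smaller of lost and gained), with X ~ Binomial(lost + gained, 0.5).

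| PED at Baseline → later | Lost | Gained | Exact p |
|---|---|---|---|
| 98 → 85 | 13 | 0 | 0.0002 |
| 98 → 85 | 25 | 12 | 0.047 |
| 98 → 85 | 37 | 24 | 0.12 |
| 98 → 92 | 6 | 0 | 0.031 |
| 98 → 92 | 7 | 1 | 0.070 |
| 98 → 92 | 18 | 12 | 0.36 |

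The 6/0 row is 2 × 1/2^6 = 0.031. The 7/1 row is 2 × (1 + 8)/2^8 = 18/256 = 0.070.

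Within each block the by-visit percentages are identical (80.3% then 69.7%; 80.3% then 75.4%), yet the paired results differ. Some rows are extreme: 24 gained means every PED-free eye gained a PED, and 12 gained means half did. The 7/1 row is not extreme. The table shows only that marginal percentages do not determine paired change; it does not predict this trial's data.

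**The case against.** Several objections are sound, and they set the limits of the point.

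- **A reader might infer that within-eye change in PED is never analysed.** The documents do not support that. SAP 6.3.1 categorises, tabulates and models change in PED type from Baseline to the last measurement up to Week 16. What is missing is paired change in presence anywhere, and any paired PED analysis for the secondary endpoint.
- **A reader might infer that the handling of PED is undisclosed.** It is not. SAP 1.1 says presence will be summarised and type described. What is absent is a statement that the protocol's McNemar rule is set aside, and why.
- **A reader might infer that by-visit percentages drift because ungradable eyes drop out.** SAP 4.1 bases percentages on total values, and UNG/P and UNG/Q are reported as categories, so those eyes stay in the denominator. The paired table is the more exposed to gradability. Differing attendance is a real issue mainly for the regimen-dependent visits, since Weeks 4, 8, 12, 16 and 48 are mandatory.
- **A reader might infer that the protocol requires a McNemar test for PED type.** The rule covers dichotomous parameters, and type has five gradable categories.

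It is also fair to say that net change to Week 48 is still reported, so the endpoint component is partly delivered, and that the study makes no multiplicity adjustment on which a conclusion about PED would rest.

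None of this explains why PED presence, coded like the six listed variables and named in the same endpoint, does not get the analysis they get.

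**Conclusion.** The point holds for PED presence. It is a named component of secondary endpoint 2, it falls under the protocol's McNemar rule, and SAP 6.3.2.2 omits it from the paired analysis without a reason. For PED type the point is narrower: within-eye change is analysed only as a primary-model predictor up to Week 16, with no category for PED absent, gained or lost, and the protocol does not require a test for it.

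The consequence is modest. Counts of eyes losing and gaining a PED, and a test of the balance, would be missing for one component of one secondary endpoint in a single-arm study. The primary outcome, sample size and safety analyses are unaffected. This conclusion rests on the text of the two documents; the p-values above use assumed counts and are illustration only. It is worth correcting because it is specific and cheap.

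**What to change.** 1. In SAP 6.3.2.2, add presence of PED (No/Yes) to the variables that receive a shift table and McNemar test at each post-baseline visit versus Baseline.
2. Add a descriptive shift table of PED type at the same visits, with a 'no PED' row and column and all five types, including purely serous. Do not apply a McNemar test to type.
3. Keep the by-visit frequencies, with UNG/P and UNG/Q shown, next to the paired tables, and report the number of eyes gradable at both visits.
4. If the sponsor prefers description only, say so in SAP 1.1 as a departure from protocol 12.5.1 and give the reason.

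The cost is two extra tables per visit from data already graded. There are two downsides. One is another unadjusted test at each post-baseline visit, at most 12 by the visit schedule (visits 3 to 14). The other is that the paired tables drop eyes ungradable at either visit, which is why item 3 is needed.

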6.3.2.3. Best corrected visual acuity (BCVA)

Definition

The visual acuity is assessed by means of Best corrected visual acuity (BCVA). BCVA measurements will be taken in a sitting position using Early Treatment Diabetic Retinopathy Study (ETDRS) like visual acuity testing charts at an initial testing distance of 4 meters. The ETDRS chart has been established as the gold standard for objective VA measurement in clinical trials and consists of 14 rows of 5 letters each, for a total of 70 letters. A higher score represents better vision. BCVA will be assessed in the study eye at every study visit and in the fellow eye at Screening and Week 48. Only assessment on the study eye will be considered in the analysis.

Analysis methodology

BCVA ETDRS score in the study eye will be summarized at each visit by means of descriptive statistics for continuous variable together with absolute changes from baseline. A paired t-test or Wilcoxon signed rank test, based on data distribution, will

| | |
|--|----------------------------------|
| | Statistical Analysis Plan |
| | Sponsor: Novartis |
| | Protocol: CRTH258AIT04 |

be used to test the BCVA ETDRS score difference at each time point vs Baseline. A spaghetti plot of BCVA ETDRS score at each timepoint will be provided by type of predominant CNV lesion (of note, 'UNG/Q' and 'UNG/P' evaluation of predominant CNV lesion will be considered in a unique category 'Ungradable').

In addition, considering each post-baseline visit, the proportion of patients with improvement of at least 5, 10 and 15 letters in BCVA ETDRS score (i.e., absolute change greater or equal to 5, 10 and 15, respectively) will be provided. Similarly, the proportion of patients with worsening of at least 5, 10 and 15 letters in BCVA ETDRS score (i.e., absolute change less or equal to -5, -10 and -15, respectively) will be summarized.

The same analyses will be also repeated focusing on patients with BCVA ETDRS score at baseline lower than 69 letters.

Data handling rules

Firstly, an observed approach will be considered for all the analysis and the LOCF approach will be also applied but focusing only until Week 16 since after this timepoint the scheduled of visits will be different for each patient according to treatment regimen assigned.

Sensitivity of secondary analysis

Not applicable.

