8.2 Participant demographics/other baseline characteristics

The following information will be collected/documentated at Screening/Baseline visit for each participant:

- Age (Screening)
- Sex (Screening)
- Race/Ethnicity (Screening)
- Vital signs, i.e. sitting blood pressure (systolic and diastolic pressure in mmHg) and pulse rate (beats per minute) (Screening and Baseline). Of note, in case there is an elevated blood pressure measurement as specified in the exclusion criteria, at Screening, the blood pressure measurement should be repeated after 20 minutes. If the repeat measurement is elevated as specified in the exclusion criteria, then the patient is not eligible to be enrolled into the study.

- Pregnancy test results for all women of childbearing potential (Screening and Baseline)
- Visual acuity (BCVA) (Screening and Baseline)
- Complete ophthalmic examination (Screening and Baseline)
- Retinal imaging (SD-OCT, OCTA and 3-field CFP at Screening and Baseline; FA and ICGA at Screening)
- EQ-5D-5L questionnaire (Baseline)
- HADS questionnaire (Baseline)
- Prior/concomitant medications (all prescription medications, over-the-counter drugs and significant non-drug therapies must be documented. See [Section 6.2.1](#) for further details) (Screening and Baseline)
- Medical history and current medical conditions (Screening)

Investigators will have the option to record abnormal test findings on the medical history eCRF page whenever, in their judgment, the test abnormality occurred prior to the informed consent signature.

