Participants who sign an informed consent form and subsequently found to be ineligible will be considered a screen failure. The reason for screen failure should be recorded on the appropriate eCRF page. The demographic information, informed consent, and Inclusion/Exclusion eCRF pages must also be completed for screen failure participants. No other data will be entered into the clinical database for participants who are screen failures, unless the participant experienced a serious adverse event (SAE) during the screening phase.

Definition of Baseline

Baseline date (day 1) is defined as the date of the first treatment administration, i.e. the date of Visit 2.

First/Last Administration of Study Treatment

The date of first brolucizumab administration is the first date of injection reported in the BROLUCIZUMAB DOSAGE ADMINISTRATION RECORD eCRF page.

The date of last brolucizumab intake is the last treatment date reported in the TREATMENT DISPOSITION eCRF page.

Study day

| | |
|--|---|
| | Statistical Analysis Plan |
| | Sponsor: Novartis Protocol: CRTH258AIT04 |

Study day is defined as the number of days from the first treatment administration date (i.e., reference date) to the visit/event date. If the visit/event date is on the same day of after the reference date, it is calculated as:

Study day = Visit/event date - first brolucizumab administration date + 1 day.

If the visit/event date is before the first brolucizumab injection date, then the study day is calculated as follows:

Study day = Visit/event date - first brolucizumab administration date.

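### In the added BCVA <69 analyses, one Visit 2 reading both selects the eyes and anchors their change, so part of the subgroup's gain is regression to the mean

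*SAP*

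**What the plan says.** SAP 6.3.2.3 has the study-eye score "summarized at each visit by means of descriptive statistics for continuous variable together with absolute changes from baseline". Depending on the distribution, either the signed rank test or the t-test for pairs is to "be used to test the BCVA ETDRS score difference at each time point vs Baseline". It also tabulates "the proportion of patients with improvement of at least 5, 10 and 15 letters in BCVA ETDRS score", with the matching losses. The section then adds the subgroup: "The same analyses will be also repeated focusing on patients with BCVA ETDRS score at baseline lower than 69 letters". SAP 1.1 lists this among the analyses added to the protocol. No sensitivity analysis is planned for BCVA.

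The reference is a single visit. SAP 4.2 states: "Baseline date (day 1) is defined as the date of the first treatment administration, i.e. the date of Visit 2". A second pre-treatment score exists, because Protocol 8.2 lists "Visual acuity (BCVA) (Screening and Baseline)" and Protocol 3 allows a screening period of up to two weeks. SAP 4.2 has one exception. Where Screening and Baseline took place on the same day, the Baseline result also serves as the Screening result.

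**The concern.** A visual acuity score is a true level plus reading error. Keeping only scores below a cut-off on one reading over-represents eyes whose error was negative that day. At the next visit the error is drawn afresh, so the average rises even if no eye has changed. Here the selected reading is also the one subtracted, so the rise goes straight into the change score. It always points towards improvement.

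The analysis serves a secondary objective worded as the effect of brolucizumab on functional parameters, in a study with no control arm. A reader comparing the subgroup with the full set could take a larger gain in the subgroup as a finding about eyes with poorer vision, when some of it comes from the selection rule.

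**Working it through.** The plan gives no figure for this analysis, so there is none to reproduce.

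**Inputs from the documents:** cut-off 69 letters and change measured from Visit 2 (SAP 6.3.2.3, 4.2); 122 enrolled and no control arm (SAP 3.1); two-sided 0.05 without adjustment (SAP 4.1); BCVA of at least 23 letters at both pre-treatment visits (Protocol 5.1).

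**Assumptions, because the documents are silent:** baseline mean m = 60 or 65 letters; total SD s = 14; reading-error SD w = 3, 5 or 7, independent between visits; no true change.

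**Mean artefact.** With a = (69 − m)/s,

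E[later − Baseline | Baseline < 69] = (w²/s) × φ(a)/Φ(a).

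- m = 60: a = 9/14 = 0.643, φ/Φ = 0.439
- m = 65: a = 4/14 = 0.286, φ/Φ = 0.625
- w²/s = 9/14 = 0.643, 25/14 = 1.786, 49/14 = 3.5

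**Letter-gain rates.** In the full set the change has SD w√2, so P(gain ≥ k) = 1 − Φ(k/(w√2)). Subgroup rates come from simulating the same model. Each range covers m = 60 to 65.

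| w | Mean artefact (letters) | ≥5 letters: full set → subgroup | ≥15 letters: full set → subgroup |
|---|---|---|---|
| 3 | 0.28–0.40 | 11.9% → 13.2–13.8% | 0.0% → 0.0% |
| 5 | 0.78–1.12 | 24.0% → 27.2–28.8% | 1.7% → 2.1–2.3% |
| 7 | 1.5–2.19 | 30.7% → 35.8–38.3% | 6.5% → 8.1–9.0% |

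The rise in gains of at least 5 letters runs from 13.2 − 11.9 = 1.3 to 38.3 − 30.7 = 7.6 points. For at least 15 letters it is at most 9.0 − 6.5 = 2.5 points. Rounding to whole letters and applying the 23-letter floor raises the full-set rates of at least 5 letters to about 14.5/26/32%. The mean artefact hardly changes (at most 2.25 letters), and the largest rise for at least 15 letters becomes 10.0 − 7.1 = 2.9 points.

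**Paired test.** This used 1,500 simulated trials of 122 per scenario. With m = 60, s = 13, w = 4, about 91 eyes are selected and the artefact is +0.5 letters. A false significant gain occurs in 14% of trials against a nominal 2.5% in that direction, or 6% if true individual changes vary with SD 10. In a deliberately unfavourable case (m = 65, s = 10, w = 6) the figures are +2.1 letters, 61% and 30%.

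**Selecting on Screening BCVA < 69 instead.** The mean artefact is 0.0 letters to within 0.06, the letter-gain rates return to the full-set values, and false significant gains fall to about 2 to 3%. Expected subgroup size is unchanged.

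**How many eyes move.** The correlation of the two readings is ρ = 1 − w²/s². The share on opposite sides of 69 is 2[Φ(a) − Φ₂(a, a; ρ)], where Φ₂ is the bivariate normal distribution function. This gives 8% (w = 3, m = 60) to 22% (w = 7, m = 65), or about 10 to 27 of 122.

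**Scores capped at 70.** Repeating the grid with recorded scores stopped at 70 gives a mean artefact of 0.2 to 1.4 letters.

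**The case against.** The strongest reply is about weight. This is an added subgroup analysis, the primary endpoint is untouched, and the BCVA analysis without the cut is reported beside it. No decision rule depends on the subgroup. That stands, and it limits how much the point matters.

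The size rests wholly on assumptions. That also stands: the direction is certain, the size is not. Most spurious gains of at least 5 letters would occur without any cut; with w = 5, reading error alone gives 24% in the full set and the cut adds 3 to 5 points.

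Selecting by Baseline severity is also a natural descriptive question. It is, but the section tests change as well as describing it, and gives no caveat.

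Two wider readings are tempting, and the documents do not support them:

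- **CST.** SAP 6.3.2.2 uses the same subgroup: "CST will also be described considering only patients with BCVA ETDRS score lower than 69 letters at baseline". There the eyes are selected on BCVA and the outcome is thickness, a different measurement, and the subgroup analysis is descriptive. It does not share this selection problem and could be touched only through any correlation between the two.
- **Score scale.** SAP 6.3.2.3 says the chart "consists of 14 rows of 5 letters each, for a total of 70 letters". A reader might infer that the cut-off removes only scores of 69 and 70 and is therefore meaningless. The sentence describes the chart and states no maximum score. The score range behind the cut-off needs a separate clarification; it does not support this point, and a cap at 70 would make the artefact smaller.

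**Conclusion.** The concern holds for the BCVA analyses in SAP 6.3.2.3 and the matching bullet in 1.1. Part of the subgroup's mean gain, paired-test result and rate of gains of at least 5 letters will be regression to the mean. Under the stated assumptions that part is about 0.3 to 2.2 letters and 1 to 8 percentage points, with little effect on gains of at least 15 letters.

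A reader might go further and infer that the subgroup's improvement as a whole is an artefact. The documents do not support that. They give no retest error from which to fix the size, the artefact exceeds 1.5 letters only towards the noisy end of the assumed range, and any true gain adds to it. The point merits correction because the bias runs only towards benefit, nothing in the plan removes it, and a second reading is already collected.

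**What to change.** In SAP 6.3.2.3 and the BCVA part of the bullet in 1.1, define the BCVA subgroup by Screening BCVA below 69 letters and keep change from Baseline as the outcome. Alternatively, keep the Baseline-defined subgroup, report the Screening-defined version beside it, and note that the former is subject to regression to the mean. State how many patients had Screening and Baseline on the same day, and exclude them or show them separately, because the SAP 4.2 rule leaves them with one reading. The CST analysis in 6.3.2.2 need not change on this ground. As a separate clarification, state the range of the recorded BCVA score.

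The cost is a changed definition, a footnote and one re-run on data already held. Some patients change subgroup (about 8 to 22% under the assumptions above), although its expected size does not. The correction assumes independent reading errors at the two visits and little true change in the up to two weeks between them.
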